6.5.3.3 Handling of other study treatment

Not applicable.

6.5.4 Disposal and destruction

The study drug supply can be destroyed at the local Novartis facility or third party, as appropriate, or locally at the site only if permitted by local regulations and authorized by Novartis.

7 Visit schedule and assessments

7.1 Study flow and visit schedule

Table 7-1 lists all of the assessments and indicates with an “X” the visits when they are performed. Each treatment cycle is 28 days (the 28 days cycle length is fixed regardless of whether the dose of LDK378 is withheld). All visits are to be scheduled according to the appropriate number of calendar days from Cycle 1 Day 1 of study drug administration. A visit window of +/- 1 day in Cycle 1 and +/- 3 days in Cycle 2 onwards is allowed. Imaging evaluations may be performed +/-7 days of the due date of the assessment. **Note: If treatment with LDK378 is withheld at any time during the study, all study visits, safety and efficacy assessments should continue according to the appropriate number of calendar days from Cycle 1 Day 1 as per the schedule of assessments.**

All data obtained from these assessments must be supported in the patients’ source documentation. No eCRF will be used as a source document. The table indicates which assessments produce data to be entered into the database (D) or remain in the source documents only (S).

Table 7-1 Visit evaluation schedule

	Category	Protocol section TBC	Screening Phase	PK Run-In Phase ^{a,b}	Treatment Phase						Post-treatment efficacy follow-up if no PD at the EOT	Survival follow-up	
					Cycles 1 (28 d)			Subsequent cycles (28 d)	End of study treatment (EOT)				
Visit name			Screening Visit (Day -28 to Day -1)	Run-In Day 1	Run-In Days 2, 3, 4 and 5	Cycle 1, Day 1	Cycle 1, Day 8	Cycle 1, Day 15	Cycle 2, Day 1; Cycle 3, Day 1; etc.	End of treatment visit	Tumor follow-up	End of post-treatment study phase	Survival follow-up
CT scan or MRI of other metastatic sites (e.g. neck, pelvis, etc) Localized bone CT scan, MRI or x-ray (for any lesions identified on the whole body bone scan that are not visible on the chest/abdomen CT scan or MRI) Photography (for any skin lesions)	D	7.2.1	X (if clinically indicated)						Cycles 3 then every 2 nd cycle (i.e. every 8 weeks): only if positive at baseline or clinically indicated	Only if positive at baseline or clinically indicated	Every 8 weeks following EOT until PD (only if positive at baseline or clinically indicated)		

7.1.1 Molecular screening

Histologically or cytologically confirmed diagnosis of locally advanced or metastatic NSCLC that carries an ALK rearrangement, defined as positive using the FDA approved Vysis ALK Break Apart FISH Probe Kit (Abbott Molecular Inc.) test and scoring algorithm (including positivity criteria) or positive as assessed by the CFDA approved immunohistochemistry (IHC) test (Ventana Medical Systems, Inc) using rabbit monoclonal primary antibody assay (D5F3) and associated scoring algorithm. If documentation of ALK rearrangement is not available as described above, a test to confirm ALK rearrangement must be performed using an archival tumor obtained at or since the time of diagnosis or a new tumor biopsy obtained prior to the first LDK378 dose. The test will be performed at a Novartis designated central laboratory (by IHC test using rabbit monoclonal primary antibody assay (D5F3), Ventana Medical Systems, Inc). Patients must wait for the result of the ALK rearrangement status before initiating treatment with LDK378.

7.1.1.1 Tumor sample requirements for central laboratory analysis

The Informed Consent Form (ICF) will allow for a tumor sample to be collected and shipped to a Novartis-designated central laboratory for analysis. Archival tumor tissue (block or slides) and/or a fresh tumor biopsy will be tested for ALK rearrangement and will be used to determine study eligibility for patients that do not have available documentation of ALK rearrangement at Screening. Acceptable archival tumor tissue may consist of a formalin fixed paraffin embedded (FFPE) block tumor tissue or at least 7, preferably 15, slides 4-5 μ m thick. Archival specimens must be submitted with a copy of the corresponding pathology report. Results of the assay will be sent to the site. If delays are experienced in processing the sample, the screening site will be informed.

If a tumor tissue block is provided, the remaining tissue will be returned to the site upon request.

If both archival and fresh tumor tissue is made available for analysis, ALK status testing will be conducted using the fresh specimen and the archival tumor tissue will be used for exploratory studies. If biopsies from multiple tumor sites are available, the primary (vs. metastatic) tumor is the preferred sample for ALK status testing.

7.1.2 Screening

Written informed consent must be obtained before any study specific procedure is performed. Screening assessments to confirm eligibility into the main study should be performed as per the schedule of assessments. Patients that do not have available documentation of ALK rearrangement at Screening must wait for result of the ALK rearrangement status before initiating treatment with LDK378.

Re-screening of patients will not be allowed, but laboratory parameters which do not meet the inclusion criteria may be re-tested within the screening window (Day -28 to Day -1). Laboratory assessments performed as part of the screening evaluations will not be required to be repeated prior to dosing (except urine pregnancy test). The cardiac eligibility criteria should be assessed with the central ECG report. Tumor imaging assessments will be performed at screening between Day -28 and Day -1. Any imaging assessments already completed during the regular work-up of the patient within 28 days prior to start of treatment, including before signing the main study ICF can be considered as the baseline images for this study.

7.1.2.1 Eligibility screening

Following registering in the IRT for screening, patient eligibility will be checked once all screening procedures are completed. The eligibility check will be embedded in the IRT system. Please refer to and comply with the detailed guidelines in the IRT manual.

7.1.2.2 Information to be collected on screening failures

Patients who sign an informed consent but fail to be started on treatment for any reason will be considered a screening failure.

The following eCRFs must be completed for screening failure patients:

- Screening Phase Disposition page (including reason for not being started on treatment)
- Informed consent
- Demography
- Adverse Events (only if an SAE occurs)
- Inclusion/Exclusion criteria

7.1.2.3 Patient demographics and other baseline characteristics

Data to be collected on patient characteristics at screening include:

- Demography (including: date of birth, age, patient initials, gender, childbearing potential, race and ethnicity, or as allowed by local regulations)
- Relevant medical history
- History of smoking
- NSCLC diagnosis and extent of disease, including:
 - Date of diagnosis of NSCLC
 - ALK status documentation
 - Site of active disease
 - Characteristics of disease
- Prior antineoplastic therapies (medications, radiation, surgeries)

- Prior and Concomitant Medications, surgical and medical procedures

All other medications taken within 28 days before the first dose of study treatment is administered must be recorded on the Prior and Concomitant medication eCRF page and updated on a continual basis if there is new change to the medication.

7.1.3 PK Run-in period

The first 15 patients enrolled will participate in a single-dose PK run-in period. Additional patients may be enrolled in the study with PK run-in period in case PK profiles from some of the enrolled patients are deemed not evaluable due to early discontinuation from the study or due to vomiting events on the day of PK sampling. In order to characterize the pharmacokinetics of LDK378 in Chinese patients, a single-dose PK run-in period of 5 days will be completed. Since the Cycle 1 Day 1 pre-dose PK collection is considered the 120 hours post-dose PK time point of the PK run-in period, if possible, Cycle 1 Day 1 should immediately follow the 5-day PK run-in phase. If a break between Day 5 of the PK run-in period and Day 1 of Cycle 1 occurs, a 120 hour post-dose PK sample should be collected on the 6th day of the PK run-in phase and no pre-dose PK sample should be collected at Cycle 1 Day 1.

For details of assessments during the PK run-in period, refer to [Table 7-4](#).

7.1.4 Treatment period

The study treatment phase begins on Cycle 1, Day 1 with the first administration of LDK378 and will continue until unacceptable toxicity that precludes further treatment, start of a new anti-cancer therapy, treatment is discontinued at the discretion of the investigator and/or patient death. If a patient experiences disease progression (radiologically documented according to RECIST 1.1 by investigator assessment), LDK378 administration may be stopped, or may be continued if the patient is continuing to derive clinical benefit in the opinion of the investigator.

Patients will be assessed as per visit schedule in [Table 7-1](#).

Visit windows of \pm 1 calendar day will be applicable to scheduled study assessments during Cycle 1. Visit windows of \pm 3 days from scheduled study assessments will apply during and beyond Cycle 2. The only exception is imaging assessments, which have a \pm 7 day window at all scheduled time points.

7.1.5 Discontinuation of study treatment

A patient will be defined as on the study if they are continuing to have any study data collected, i.e. if the patient is being treated with LDK378, is in efficacy follow-up after discontinuing LDK378, or is in survival follow-up.

Patients may voluntarily withdraw from study treatment for any reason at any time. In this situation, the patient should be encouraged to consent to be followed for tumor assessments until the development of Progressive Disease (as assessed by investigator) and/or survival. If a patient decides to discontinue from the study treatment, the investigator must make every effort (e.g. telephone, e-mail, letter) to determine the primary reason for this decision and

record this information in the patient's chart and on the appropriate CRF pages. They may be considered withdrawn if they state an intention to withdraw, fail to return for visits, or become lost to follow-up for any other reason.

The investigator should discontinue study treatment for a given patient if, on balance, he/she believes that continuation would be detrimental to the patient's well-being.

Patients must permanently stop the study treatment if one of the following occurs:

- Pregnancy
- Study Terminated by Sponsor
- Patient/guardian decision
- Physician decision
- Lost to follow-up
- Death

Patients may permanently stop the study treatment for one of the following reasons:

- Progression of disease (radiological as assessed by investigator)
- AEs
- Non-compliance with study treatment
- Technical Problems
- Use of prohibited treatment
- - Any protocol deviation that results in a significant risk to the patient's safety

Patients who become pregnant during the trial must be withdrawn ([Section 8.4](#)). Patients who become pregnant must cease all tumor assessments regardless of whether or not they developed Progressive Disease.

Patients who discontinue study treatment during the treatment phase should NOT be considered withdrawn from the study. They should be scheduled for a visit as soon as possible and within 7 days after the last dose of study treatment, at which time all of the assessments listed for the EOT visit will be performed. If a patient withdraws from treatment at a study visit, EOT assessments do not need to be repeated. An End of Treatment Phase Disposition eCRF page should be completed, giving the date and reason for stopping LDK378 treatment.

Patients who have RECIST-defined PD by investigator assessment, but who, in the opinion of the investigator, have evidence of continued clinical benefit from LDK378 may continue to receive this drug. These patients will continue assessments as detailed in [Table 7-1](#) except tumor and [REDACTED]. In such cases, patients must complete the EOT visit only after permanent discontinuation of LDK378. An End of Treatment Phase Disposition eCRF page should be completed, giving the date and reason for stopping the study treatment.

At a minimum, all patients who discontinue study treatment, including those who refuse to return for a final visit, will be contacted for safety evaluations during the 30 days following the last dose of study treatment.

If patients refuse to return for these visits or are unable to do so, every effort should be made to contact them or a knowledgeable informant by telephone to determine the survival status.

[REDACTED]

[REDACTED]

[REDACTED]

[REDACTED]

Patients who discontinue study treatment should be considered withdrawn from the study after the final visit assessments are performed or when it is clear that the patient will not return for these assessments. They may be considered withdrawn if they state an intention to withdraw, fail to return for visits, or become lost to follow-up for any other reason.

If a patient discontinues study treatment, but continues study assessments, (e.g. during post treatment follow up phase as detailed in [Table 7-1](#)), the patient remains on study until such time as he/she completes protocol criteria for ending study assessments. At that time, the reason for study completion should be recorded on the End of Post Treatment (Study Phase Completion) Disposition eCRF page.

If using IRT, the Investigator must contact the IRT to register the subject's discontinuation from treatment.

Patients who discontinue study treatment should enter the survival follow-up period or continue tumor assessments when appropriate. Tumor assessments will continue until the investigator assessment determined disease progression, patient withdraws consent from tumor assessments patient is lost to follow-up, death or study terminated by Sponsor.

If a patient will have no further study data collected because he/she withdraws from the study completely, the investigator must determine the primary reason for a patient's premature withdrawal from the study and record this information on the Study Phase Completion Disposition eCRF as applicable. The investigator must show "due diligence" by documenting in the source documents steps taken to contact the patient, e.g., dates of telephone calls, registered letters, etc. They may be considered withdrawn if they state an intention to withdraw, fail to return for visits, or become lost to follow-up for any other reason. If the patient was still taking study medication at the time of the withdrawal, the End of Treatment eCRF should also be completed.

Patients may voluntarily withdraw from the study or be discontinued from the study at the discretion of the investigator at any time.

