7.1.6 Withdrawal of Consent

Patients may voluntarily withdraw consent to participate in the study for any reason at any time. Withdrawal of consent occurs only when a patient does not want to participate in the study any longer, and does not want any further visits or assessments, and does not want any further study related contact.

Novartis will continue to retain and use all research results that have already been collected for the study evaluation. All biological samples that have already been collected may be retained and analyzed at a later date (or as required by local regulations).

If a patient withdraws consent, the investigator must make every effort (e.g. telephone, e-mail, letter) to determine the primary reason for this decision and record this information. Study treatment must be discontinued and no further assessments conducted.

Further attempts to contact the patient are not allowed unless safety findings require communication or follow up.

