7.1.7.4 Lost to follow-up

For patients whose status is unclear because they fail to appear for study visits without stating an intention to withdraw consent, the investigator should show "due diligence" by contacting the patient, family or family physician as agreed in the informed consent and by documenting in the source documents steps taken to contact the patient, e.g. dates of telephone calls, registered letters, etc. A patient should not be considered lost to follow-up until due diligence has been completed. Patients lost to follow up should be recorded as such on the appropriate Disposition CRF.

[REDACTED]

[REDACTED]

[REDACTED]

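### Section 7.1.5 tells sites both that stopping treatment is not withdrawal and that it becomes withdrawal after the final visit, which puts post-treatment PFS, DOR and OS data at risk

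*Protocol*

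**What the plan says.** All of the conflicting text is in the current body of Protocol Section 7.1.5, not in the amendment log.

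- The section opens by defining study status by data collection: "A patient will be defined as on the study if they are continuing to have any study data collected". Efficacy follow-up and survival follow-up both count.
- It then says: "Patients who discontinue study treatment during the treatment phase should NOT be considered withdrawn from the study".
- Further on, about the same patients: "Patients who discontinue study treatment should be considered withdrawn from the study after the final visit assessments are performed", or once it is clear that they will not come back for those assessments.
- One sentence appears three times in the section: "They may be considered withdrawn if they state an intention to withdraw, fail to return for visits, or become lost to follow-up".
- Still in 7.1.5, patients who stop treatment are sent to survival follow-up or to continued tumor assessments, and a patient who continues assessments stays on study.

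Elsewhere, Sections 4.1, 7.1.7.2 and 7.2.1.2 require scans every 8 weeks until progression for patients who stop without it. Section 7.1.7.3 requires survival contact every 12 weeks.

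**The concern.** A site with a patient who stops LDK378 for toxicity, without progression, can find authority in one section for two different actions. It can keep the patient on scans and survival contact, or it can record the patient as withdrawn once the last visit is done. The missed-visit sentence widens the second route.

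PFS, DOR and OS all need data from after treatment stops. A patient closed at that point contributes no later progression or death. Stopping treatment and missing visits are plausibly related to prognosis, so the resulting censoring may be informative. If so, the Kaplan-Meier curves would probably read too high.

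**Working it through.** The plan states no dropout or closure rate, so there is no planned figure to reproduce. The check is mainly a comparison of text.

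**1. Same patients, same force.** The two sentences cover the same group (patients who stop study treatment), and both use 'should'. Nothing ranks one above the other.

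**2. What the final visit is.** The term is not defined in the visible text. Section 7.1.5 also uses it for patients who refuse to attend it but are still contacted in the 30 days after the last dose, which points to the end-of-treatment (EOT) visit. The glossary entry *Stop study participation* leans the same way: it takes the later of the final evaluation visit and the end of dosing. If the term meant the last follow-up visit, the conflict would shrink for patients who attend. The second limb, closing patients who will clearly not return, would remain.

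**3. Missed visits.** Section 7.1.6 is narrow: "Withdrawal of consent occurs only when a patient does not want to participate in the study any longer", and it adds refusal of further visits and of contact. Section 7.1.7.4 says: "A patient should not be considered lost to follow-up until due diligence has been completed". A patient who has only missed visits meets neither test, yet 7.1.5 allows the withdrawn label. The third use of the sentence follows a due-diligence requirement, in a paragraph about complete withdrawal. The first two uses carry no such condition.

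**4. What happens to a closed patient in the analysis.** SAP Section 3.2.4 has a disposition category for patients who leave the study from the treatment phase with no next phase and no survival follow-up. Under SAP Section 3.2.10.2 such a patient, if event-free, is censored for PFS and DOR at the last adequate tumor assessment. For OS the patient is censored at last contact and labelled lost once the gap to cut-off exceeds 18 weeks.

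**5. Who could be affected.** The Amendment 3 rationale gives 103 treated, 66 off treatment and 37 on treatment. 66/103 = 64.1%. This is a ceiling at that date. Patients who had progressed needed no more scans, and patients who had died had nothing left to lose. The 66 are not broken down by reason.

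**6. End-of-study trigger (Section 4.3).** 0.75 × 103 = 77.25, so 78 patients. It counts deaths, losses to follow-up, and withdrawals of consent to survival follow-up.

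**7. Illustration of direction, not an estimate.** The assumptions are:
- time on treatment exponential with median 6.9 months (the prior-study median PFS in Section 2.1, as a stand-in);
- no deaths on treatment;
- survival after stopping exponential with median 4, 8 or 12 months;
- cut-off at 30 months;
- a share of patients closed 0.25 month after stopping.

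Each cell gives Kaplan-Meier median OS in months, then deaths captured per 103 patients.

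| Median survival after stopping | None closed | 10% closed | 30% closed |
|---|---|---|---|
| 4 months | 12.97; 91.9 | 13.56; 83.1 | 15.07; 65.5 |
| 8 months | 18.0; 79.0 | 18.6; 71.2 | 20.13; 55.9 |
| 12 months | 22.51; 67.0 | 23.14; 60.3 | 24.68; 47.3 |

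The median rises by about 0.6 month at 10% closed and 2.1 to 2.2 months at 30%. Because the model puts all deaths after treatment stops, it exaggerates the dependence.

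**The case against.** The strongest reply is that one stray sentence stands against the rest of the protocol, and a careful site would not follow it.

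- Section 7.1.5 itself requires safety contact for 30 days after the last dose, and every effort to learn survival status when a patient will not attend.
- The glossary entry *Premature patient withdrawal* leaves room for progression and survival follow-up after withdrawal.
- Section 7.1.7.3 follows for survival even patients who have withdrawn consent to further assessments, and the eCRF records survival follow-up as a separate question.
- The missed-visit sentence says only 'may'.
- The documents report no patient closed early.

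The effect on the trial is also limited. The primary objectives are PK and safety, and Section 10.10 disclaims formal testing. ORR is largely protected because Appendix 2 by default excludes assessments more than 30 days after the last dose from best response. The SAP would make early closures visible through PFS censoring reasons, the 18-week OS flag and the gap analyses.

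All of this stands as a limit on the size of the problem. None of it cancels the sentence. The text that keeps a patient on study applies only to one who continues assessments, and the SAP summaries reveal missing follow-up without recovering it.

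**Conclusion.** The contradiction is real, and worth correcting because it bears on data that PFS, DOR and OS need. It creates a risk of early closure with possibly informative censoring of descriptive secondary endpoints. Its size cannot be computed from the documents.

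A reader might infer three stronger things, which the documents do not support:

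- **That follow-up is planned to stop at the EOT visit.** Sections 4.1, 7.1.7.2, 7.1.7.3 and 7.2.1.2, and other parts of 7.1.5, require it to continue.
- **That withdrawn patients bring the 75% end-of-study trigger forward.** The withdrawn label alone does not count. Only death, loss to follow-up, or withdrawn consent to survival follow-up counts. If, say, 10 or 20 closures were wrongly recorded in one of the last two ways, the trigger would fall at 68 or 58 deaths instead of 78, but 7.1.5 does not authorise that recording.
- **That a definite number of patients is lost, or that PFS and OS are biased upward by a known amount.** Applying the 10.2% stopping for adverse events in Section 1.2.1.2.1 gives 0.102 × 103 = 10.5 patients. That rate is from another study, Section 1.3 gives 8.8% (9.1 patients), and the count assumes every site follows the one outlying sentence. Any assumed closure share, including those in the illustration, has no source in the documents.

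**What to change.** In Section 7.1.5, delete the sentence that makes patients withdrawn after the final visit. Reword the three missed-visit sentences so that stopping treatment, completing the EOT visit or missing visits does not by itself end study participation.

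State that participation ends on death, withdrawal of consent as defined in 7.1.6, loss to follow-up after the due diligence of 7.1.7.4, or study end. Keep the existing pregnancy provisions in 7.1.5 and 8.4, which such a list would otherwise contradict. Reconcile two other places with it: the closing sentence of 7.1.5 on discontinuing patients from the study at the investigator's discretion, and the glossary entry *Stop study participation*.

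Send a letter to sites and check the disposition of every patient already closed. Resume scheduled follow-up for those closed only because treatment stopped or visits were missed. Do not re-contact anyone who withdrew consent under 7.1.6.

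The cost is a short amendment, a site letter, a disposition check, and contact with any patients found. The scans and survival calls are already scheduled, so no procedure is added.
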